6.4 LTE Analysis

[figure not shown]
After review of PA results, the study was terminated. The LTE analysis will occur when all subjects either completed or early terminated the study and the full database is locked.

.

7 Changes to the Planned Analyses in the Clinical Trial Protocol

- The protocol states there may be an Interim Analysis (IA) for futility based on the highest dose of M2951, triggered when 100% of subjects enrolled in the PAC reach Week 24 of treatment, or prematurely discontinue from treatment prior to Week 24. It has been decided by Merck/EMD-Serono team not to perform this IA.
- The protocol refers to the co-primary endpoints as SRI-4 Response and SRI-6 Response for HDA subjects. Instead, they will be referred as two-primary endpoints in this IAP, according to the latest FDA guidance on multiplicity.
- The protocol mentions the McNemar's test to assess the change in a binary endpoint between two timepoints. For other secondary endpoints, the test will not be performed, only descriptive statistics will be provided.
- It is no longer planned that whole blood will be analyzed for phosphoproteomics or B cell activation and these endpoints will not be reported.
- The LLDAS status as defined in Section 18.1.7 must include the $PGA \leq 1$ (0-3 scale) in the definition. This item was not mentioned in the protocol and has been added to this IAP.
- The protocol refers to the endpoint 'Changes over time in SRI response/in LDA status' for the LTE analysis but will be referred as 'SRI response/LDA status over time' in this IAP, for accuracy.
- The protocol states the PAC used for PA consists of the first 432 subjects randomized. However, due to a potentially higher than expected drop-out rate, the PAC will include all subjects screened/randomized as of November 28, 2018 ($n > 432$), to protect the power of the statistical analysis for which the sample size was calculated.
- The protocol states the definition of the subgroup severity of disease at screening (severe, mild/moderate), but a more detailed definition has been added to this IAP (see Section 8.2.3), for correctness.
- The protocol mentions a sensitivity analysis of the two-primary endpoints on completers. This analysis will not be performed as the primary analysis already considers subjects who discontinued treatment as non-responder.

CCI

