- The protocol specifies that flare-free status will be analyzed separately depending on severity, but in this IAP flare-free status is defined as not having any flares (defined with BILAG 2004 and SFI, separately) during the 52-week treatment period.
- The protocol mentions several endpoints for the analysis of corticosteroid usage over time. The first endpoint (i.e., reduction from baseline in prednisone-equivalent CS dose by $\geq 25\%$ to a dose of ≤ 7.5 mg/day, with no BILAG A or 2B flare in disease activity at that visit) is removed from this IAP. Analysis of the clinically meaningful reduction in CS dose from Baseline (defined as a reduction of daily prednisone-equivalent CS dose $\geq 25\%$ to a dose of ≤ 7.5 mg/day by Week 40 and sustained through Week 52 AND no new BILAG A organ domain scores and no more than one new BILAG B organ domain score during Weeks 40 through 52) will be sufficient.
- SRI definition specified in the protocol includes ‘no discontinuation of investigational product’, but this condition has been removed from this IAP (see Section 14.1.1). Subjects with missing response at Week 52 have been added as a condition of non-SRI responder, meaning that all subjects who prematurely discontinued treatment will be considered as non-SRI responder.
- For definition of SRI responses, LDA Definition #2, LLDAS and BICLA, EAC-treatment failure assessment will be used to consider subjects as non-responder in these 3 endpoints.
- Due to study termination, the analysis of Japanese cohort and LTE analysis will be performed simultaneously. The Japanese cohort will not be explored for consistency, the listings produced for the PA will be rerun including all Japanese subjects. A safety summary of Asia-Pacific subjects will be presented during the 52-Week treatment period (see Section 14.1.4). The LTE analysis will be reduced with a focus on safety, further details can be found in Sections 14.6 and 15.

8 Protocol Deviations and Analysis Sets

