14.1.1 Definitions

The two-primary efficacy endpoints are SRI response at Week 52:

- SRI-4 response in all subjects,
- SRI-6 response in the HDA subgroup.

The SRI-4 response, a measure of reduced SLE disease activity, is defined by meeting all of the following conditions compared to Baseline:

1. ≥ 4 -point reduction in SLEDAI-2K total score.
2. No significant worsening in PGA score (< 0.3 increase assuming the PGA score is on a 0-3 scale).
3. No new BILAG A organ domain scores and ≤ 1 new BILAG B organ domain score compared to Day 1 using BILAG 2004.
4. No institution of EAC-determined protocol-prohibited medication/treatment (i.e., EAC-treatment failure)

Subjects with missing values at Week 52 after the implementation of rules defined in Appendices 18.1.1 and 18.1.3 will be considered as non-responder in the primary analysis.

Assessment of criterion #4 will be confirmed by an Endpoint Adjudication Committee (EAC). Further details can be found in the EAC Charter.

The SRI-6 response is defined similarly to SRI-4, based on a ≥ 6 -point reduction in SLEDAI-2K total score.

Details of derivation are described in Appendix 18.1.

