14.1.2 Primary Analysis of the Two-primary Endpoints

Table 17 outlines all planned statistical analyses of the two-primary endpoints. In the context of estimands, handling the intercurrent events is also explained in the table.

Table 17 : Analysis of the two-primary endpoints

Analysis	Analysis Population	Analysis Method	Data Handling Notes and handling of intercurrent events
Two Primary endpoints / MCP	mITT Analysis Set	
 Presentation of adjusted Odds-Ratio (OR), 2-sided 95% CI of OR, nominal 1-sided p-value, adjusted 1-sided p-value ($\alpha=0.025$) from Logistic Regression Number and percentage of responders in each dose group, observed Δ in response proportions from Placebo for each dose group 	
A subject with a missing response at Week 52 will be considered a non-responder at Week 52.
 
Subjects with endpoint adjudication committee (EAC)-determined treatment failure based on protocol-prohibited medication will be considered as non-responder.
 
(Estimand: composite strategy)

Sensitivity 1 (Per Protocol Analysis)	PP Analysis Set	
 • Presentation of OR, 2-sided 95% CI of OR, nominal p-value from Logistic Regression • Number and percentage of responders in each dose group, observed Δ in response proportions from Placebo for each dose group 	Same as Primary Analysis
Sensitivity 2 (Multiple Imputation Analysis)	mITT Analysis Set	
 • Presentation of OR, 2-sided 95% CI of OR, nominal p-value from Logistic Regression • Number and percentage of responders in each dose group, observed Δ in response proportions from Placebo for each dose group 	
For subjects with missing response at Week 52, the multiple imputation (MI) will be used to impute the missing data using the available observations.
 
Subjects with endpoint adjudication committee (EAC)-determined treatment failure based on protocol-prohibited medication will be considered as non-responder.
 
(Estimand: composite strategy)

Sensitivity 3 (Tipping Point Analysis)	mITT Analysis Set	
 • Presentation of study conclusion at each possible combinations of responders from each treatment group. 	
Tipping Point Analysis
 
Subjects with endpoint adjudication committee (EAC)-determined treatment failure based on protocol-prohibited medication will be considered as non-responder.
 
(Estimand: composite strategy)

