If a subject completely missed a visit, the BILAG grades from previous analysis visit will be used and BILAG flare will be derived as missing.

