18.1.2 Physician Global Assessment

The PGA is used to quantify disease activity and is measured using an anchored VAS (see [Figure 1](#)). The PGA will be determined on a continuous VAS that asks the Investigator to assess the subject's current disease activity from a score of 0 (none) to 3 (severe), with the assessment made relative not to the subject's most severe state but the most severe state of SLE per the Investigator's assessment. As per its validation method, the PGA is recommended to be completed prior to laboratory results from the individual study visit being available ([Petri 1992](#)).

This version of the PGA is not scored blindly. The assessor is instructed to look at the previous month's PGA, decide whether the overall condition of the subject is same, better or worse and move the line accordingly.

A score change, where score is moved to the right from 2.5 or below in the previous month to > 2.5 this month, denotes an arbitrary threshold for severe flare to be considered when determining if enough change has occurred to justify assessing the criterion as severe flare. A score change ≥ 1 unit to the right denotes a designation of mild/moderate flare.

Figure 1: Physician Global Assessment Visual Analog Scale with Anchors

If a subject completely missed a visit, the PGA score from previous analysis visit will be used.

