If a subject completely missed a visit, the SLEDAI-2K total score from previous analysis visit will be used.

Change from baseline and SRI response

In general, SLEDAI clinical components are not expected to be missing.

In unlikely case of missing clinical value, change from baseline and thus SRI response (see [Section 14.1.1](#)) will be derived as follows:

- If the missing clinical component has weight > 4 in the overall score (see [Table 33](#)), then no imputation is performed. The SLEDAI-2K score will be missing and thus subject will be considered as non-SRI responder.
- If the missing clinical component has weight ≤ 4 in the overall score (see [Table 33](#)) or laboratory components missing, then the first step of imputation will be to carry forward the value of previous analysis visit (only value assessed while subject is on-treatment can be used for imputation). If that corresponding previous analysis visit value is also missing, then the component value will remain missing and the steps below will be followed:
 - Baseline SLEDAI-2K score will be re-derived with corresponding missing values at scheduled visit set to missing at Baseline visit
 - Change from baseline to analysis visit will be calculated and use as follows for SRI response derivation:
 - If there is a change from baseline ≥ 4 points reduction based on available non-missing components, then criterion #1 for SRI response is met
 - If there is an increase (i.e. worsening) or no change, or 1 to 3 points reduction based on available non-missing component, then the subject will be considered as non-SRI responder for that analysis visit

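### The SAP gives conflicting rules for a subject with no Week 52 assessment: non-responder in the main text, carried-forward scores in the appendices

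*SAP*

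**What the plan says.** Main text:

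- Table 17 (Section 14.1.2): "A subject with a missing response at Week 52 will be considered a non-responder at Week 52".
- Section 7 removes from SRI the protocol's requirement that the subject has not stopped investigational product. It adds a missing Week 52 response as a cause of non-response, "meaning that all subjects who prematurely discontinued treatment will be considered as non-SRI responder".
- Section 7 also drops the protocol's completers analysis because "the primary analysis already considers subjects who discontinued treatment as non-responder".
- Section 14.1.2.1 tabulates reasons for imputed non-response. They include treatment discontinuation (three groups) and completers whose Week 52 response is missing.

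Derivation text:

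- Section 14.1.1 sets the order: "Subjects with missing values at Week 52 after the implementation of rules defined in Appendices 18.1.1 and 18.1.3 will be considered as non-responder".
- Appendix 18.1.3, at the end of the block on actual scores: "If a subject completely missed a visit, the SLEDAI-2K total score from previous analysis visit will be used".
- Missing-data text at the end of Appendix 18.1.1.9: "If a subject completely missed a visit, the BILAG grades from previous analysis visit will be used".
- Appendix 18.1.2: "If a subject completely missed a visit, the PGA score from previous analysis visit will be used".

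A separate block of Appendix 18.1.3, on change from baseline and SRI response, has no whole-visit sentence. It makes the SLEDAI-2K score missing, and the subject a non-responder, when a clinical item of weight above 4 is missing.

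**The concern.** The non-responder rule protects the primary endpoints only if Week 52 is still missing when the rule is reached. The appendix rules run first and can fill all three scored components of SRI. With the discontinuation criterion gone, Section 14.1.1 contains nothing else that makes a subject without Week 52 data a non-responder, apart from treatment failure determined by the Endpoint Adjudication Committee (EAC).

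At stake is who counts as a responder on both primary endpoints and on the first key secondary endpoint, which uses the same SRI-4 derivation. LDA and LLDAS follow the primary handling (Table 19) and use the actual SLEDAI-2K score directly. BICLA (Appendix 18.1.8) cites the same two appendices. Two programmers working from this text could produce different primary results.

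**Working it through.** **The plan's own figure.** Section 8.2.1 states 80% power, or 76% if the SRI-6 improvement is 20 points. At one-sided 0.0125, power is 0.740 for 40% against 60% with 103 per arm, and 0.631 for 30% against 55% with 51.5 HDA subjects per arm (0.431 against 50%). Power for at least one success under Hochberg, at an assumed correlation of 0.8 between the endpoints, is 0.801 and 0.760. The stated figures are reproduced, and the present point does not depend on them.

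**Order of operations, read literally.** Take a subject still on study, with Week 48 data, no assessment in the Week 52 window and no EAC treatment failure.

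1. The SLEDAI-2K total is taken from Week 48 (18.1.3), so SRI criterion 1 can be derived.
2. PGA is taken from Week 48 (18.1.2), so criterion 2 can be derived.
3. BILAG grades are taken from Week 48 (18.1.1), so criterion 3 can be derived.
4. Nothing is left missing for the rule in 14.1.1. The subject is a responder if the Week 48 values qualify.

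**Readings the text allows (no EAC treatment failure).**

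| Reading | On study, Week 48 seen, Week 52 missed | Discontinued, last seen before Week 48 |
|---|---|---|
| Section 7 and Table 17 | Non-responder | Non-responder |
| SRI block of 18.1.3 applied to a missed visit | Non-responder | Non-responder |
| 14.1.1 taken strictly (18.1.2 not cited, so PGA stays missing) | Non-responder | Non-responder |
| Whole-visit carry-forward, one step | Scored on Week 48 | Non-responder |
| Whole-visit carry-forward, chained | Scored on Week 48 | Scored on last attended visit |

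The last two rows apply to a discontinuer only if visits after discontinuation count as missed visits, which the appendices neither state nor exclude. Chaining is not stated either. If it were used, almost nobody would be missing at Week 52, and the multiple-imputation and tipping-point analyses (14.1.2.2) would have almost nothing to act on.

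**The premise in Section 7 without carry-forward.** Table 51 assigns any assessment from Day 350 onwards, if within 14 days of last exposure, to Week 52. A subject who stops on Day 340 and is assessed on Day 352 (12 days later) has an observed Week 52 value. Missingness alone therefore does not make every discontinuer a non-responder.

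**Possible size (illustration).** In each arm, rate = (1 − m) × p + m × c, where m is the share without Week 52 data, p the response rate among those observed, and c the share of carried-forward subjects scored as responders. Non-responder handling is c = 0. Assumed, not in the SAP: p = 0.45 on placebo and 0.65 on active; c = 0.25 to 0.5, equal in both arms; about 117 per arm (469/4 = 117.25).

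| m placebo / active | Difference, c = 0 | c = 0.25 | c = 0.5 |
|---|---|---|---|
| 10% / 10% | 0.585 − 0.405 = 18.0 points | 18.0 | 18.0 |
| 15% / 25% | 0.4875 − 0.3825 = 10.5 | 13.0 | 15.5 |
| 25% / 15% | 0.5525 − 0.3375 = 21.5 | 19.0 | 16.5 |

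The change in the difference is c × (m active − m placebo). In the first row each arm gains 117.25 × 0.10 × c, or about 3 to 6 responders. At the planned 5% drop-out with an assumed 40% in response, each arm's rate rises by 0.05 × 0.40 = 2 points.

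**The case against.** A reader might infer that the primary endpoints are in effect last-observation-carried-forward endpoints, that drop-outs are scored as responders, and that this inflates the active arms by several points. The documents do not support that, for these reasons:

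- Section 7 says twice that discontinuers are non-responders, and Section 14.1.2.1 tabulates them so. This is operative text and specific to discontinuation.
- The whole-visit SLEDAI-2K sentence sits under actual scores. The SRI block makes any missing item of weight above 4 a non-response, and a wholly missed visit lacks all eight weight-8 items in Table 33.
- Section 14.1.1 does not cite 18.1.2, so a strict reader leaves PGA missing.
- The carry-forward sentences name the previous analysis visit, in the singular. For single items, the SRI block leaves the value missing if the previous visit is missing too.
- A shift of several points needs assumed rates of missingness and response. Section 7 mentions only a potentially higher drop-out rate than expected.

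All of this stands against the strong reading. It does not settle the text. The actual-scores block contains the same weight rule and still adds the whole-visit sentence, so that rule alone does not show that a missed visit escapes carry-forward. Section 14.1.1 also refers generally to Appendix 18.1, which includes 18.1.2. The BILAG and PGA sentences carry no exception. Section 7 presents non-response of discontinuers as a consequence of missingness, which is what the appendix rules may remove.

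**Conclusion.** The SAP contradicts itself on how a subject with no Week 52 assessment is scored. For a subject still on study who misses Week 52, the literal order of rules leads to carried-forward scoring. For a discontinuer this is possible but not established, because Section 7 says the opposite and the appendices do not say whether visits after discontinuation count as missed.

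Size and direction cannot be computed: the SAP gives neither missingness by arm nor the response status of those missing. The illustration shows that the difference can stay, grow or shrink, so no claim of bias in favour of evobrutinib is warranted. The wording needs correction because it determines responder status on the primary endpoints.

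**What to change.** - In 14.1.1, 18.1.1, 18.1.2 and 18.1.3, state that whole-visit carry-forward is not used at Week 52 or after treatment discontinuation for any responder endpoint (SRI, LDA, LLDAS, BICLA).
- In 14.1.1, state as an explicit rule that a subject with no assessment in the Week 52 window, or who stopped IMP before Week 52, is a non-responder. Section 7 already intends this. The disposition category for permanent discontinuation in the 52-week period (Table 7) could identify the second group.
- SAP version 4.0 postdates review of the primary analysis. The CSR should therefore report which rule was run. If carry-forward was used at Week 52, rerun the analysis under the stated non-responder rule and report it.

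The cost is SAP wording and minor programming, plus a rerun if carry-forward was used. Response rates may be slightly lower.

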14.1.2.2 Sensitivity Analyses of SRI-4 and SRI-6

The following sensitivity analyses are planned to be performed using different approaches to the missing data handling from the primary analysis.

Sensitivity Analysis #1: Per Protocol Analysis

The primary analysis method including the missing data handling approach for the two-primary endpoints will be repeated on the PP Analysis Set if the size of this analysis set differs substantially (>10%) from mITT.

For this analysis, the estimated OR, together with associated two-sided 95% CI of the estimated OR and nominal p-value from the logistic regression model, comparing each evobrutinib treatment group to placebo will be presented.

In addition, the number and percentage of SRI-4/SRI-6 responders and non-responders at Week 52 in each treatment group will be presented the same way as for the primary analysis (see Section 14.1.2.1).

Sensitivity Analysis #2: MI

In this analysis, a subject will be considered as a non-responder if using EAC-determined protocol prohibited medications (i.e., EAC-treatment failure). For subjects with missing response at Week 52, then the MI will be used to impute the missing data using the available observations from previous visits and from components of SRI-4/SRI-6 response and also stratification factor used in primary analysis.

The MI analysis will include the components as described below:

1. SLEDAI-2K change from baseline total score will be imputed using SAS MI procedure (including 2 other components: PGA score and BILAG response) and then the occurrence of a ≥ 4 -point reduction will be re-derived from the imputed values. For the SRI-6 the occurrence of a ≥ 6 -point reduction will be also re-derived from the imputed values.
2. PGA score will be imputed using SAS MI procedure (including 2 other components: SLEDAI-2K change from baseline and BILAG response), assuming the distribution is approximately normal. The imputed values will be transformed to a 0-3 scale:
 - i. Negative values will be imputed as 0,
 - ii. Values > 3 will be imputed as 3.
 - iii. The imputed score will then be used to calculate whether there was significant worsening in the PGA score.

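### The missing-item rule for SLEDAI-2K in SAP Appendix 18.1.3 states only the SRI-4 threshold, although the same rule also feeds SRI-6, a primary endpoint defined by a 6-point fall

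*SAP*

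**What the plan says.** Section 14.1.1 introduces both primary endpoints under one label: "The two-primary efficacy endpoints are SRI response at Week 52". These are SRI-4 in all subjects and SRI-6 in the HDA subgroup (screening SLEDAI-2K of 10 or more). It lists four numbered criteria for SRI-4, the first being a fall of at least 4 points, and then adds: "The SRI-6 response is defined similarly to SRI-4, based on a ≥ 6 -point reduction in SLEDAI-2K total score". It also brings the appendix into the primary analysis: subjects whose values are still missing "after the implementation of rules defined in Appendices 18.1.1 and 18.1.3 will be considered as non-responder in the primary analysis".

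The part of Appendix 18.1.3 on change from baseline refers back to Section 14.1.1 and opens: "In unlikely case of missing clinical value, change from baseline and thus SRI response". If a clinical item of weight 4 or less, or any laboratory item, is missing and the previous analysis visit cannot supply it, the item is also removed from the baseline score and the change is recalculated. Two outcomes follow:

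- "If there is a change from baseline ≥ 4 points reduction based on available non-missing components, then criterion #1 for SRI response is met".
- A fall of only 1 to 3 points, an unchanged score or a worsening on the remaining items makes the subject a non-responder at that visit.

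The multiple-imputation analysis in Section 14.1.2.2 gives SRI-6 its own cut: "For the SRI-6 the occurrence of a ≥ 6 -point reduction will be also re-derived from the imputed values".

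**The concern.** For whole-number scores the two outcomes in Appendix 18.1.3 cover every possible change. The rule is therefore not merely silent on a 4- or 5-point fall: it places such a fall on the side that meets criterion #1. That is right for SRI-4. For SRI-6 it gives the opposite result to Section 14.1.1.

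SRI-6 in HDA subjects is one of two endpoints on which the study can be declared positive, and the literal rule can only add SRI-6 responders, never remove them. The same text governs the by-visit SRI-6 rates and the SRI-4 to SRI-10 bar chart (Section 14.1.2.1), the SRI-6 secondary endpoints (Section 14.3.1) and the SRI summaries in the long-term extension (Section 14.6).

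**Working it through.** **1. The plan's own figures.** Section 8.2.1 assumes 103 evaluable subjects per group, about half of them HDA (51.5), and a one-sided 0.0125 level per endpoint. With the pooled-variance formula, power = Φ{[δ√n − z√(2p̄(1−p̄))] / √(p₁q₁ + p₂q₂)} and z = 2.241:

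- SRI-4, 40% against 60%, n = 103: 0.740.
- SRI-6, 30% against 55%, n = 51.5: 0.631. Against 50% it is 0.431.

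Power for at least one success depends on the correlation of the two test statistics, which the SAP does not state. Assumed correlations of 0.6, 0.7 and 0.8 give 0.822, 0.805 and 0.786 (the SAP states 80%), and 0.776, 0.763 and 0.751 for the 20-point SRI-6 effect (the SAP states 76%). Both figures reproduce near 0.7. Nothing in the point below changes the sample size.

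**2. A case where the two sections disagree** (weights from Table 33). An HDA subject has baseline arthritis 4, rash 2, alopecia 2 and mucosal ulcers 2, total 10, with no thrombocytopenia. At Week 52 only the arthritis has resolved. Platelets are missing at Weeks 48 and 52, so nothing can be carried forward.

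- Baseline without the platelet item: 10 − 0 = 10.
- Week 52 score on available items: 2 + 2 + 2 = 6.
- Fall: 10 − 6 = 4.

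Had platelets been measured, the fall would have been 4 (normal) or 3 (low, weight 1). It could not have reached 6. Section 14.1.1 therefore fails this subject on SRI-6 whatever the missing value was, while Appendix 18.1.3 read literally passes criterion #1.

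**3. How the branch is reached.** Eight of the 24 descriptors are laboratory items: casts, hematuria, proteinuria, pyuria, complement, anti-dsDNA, platelets and white cells. At Week 52 the item must be missing at the previous analysis visit too. At the first post-baseline visit no baseline value may be carried forward, so one missing laboratory item is enough; this affects the by-visit rates, not the Week 52 endpoint.

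**4. Size per subject.** With 51.5 HDA subjects per arm, one subject is 1/51.5 = 1.9 percentage points. Taking half of 469/4 = 117.25, that is 58.6, one subject is 1/58.6 = 1.7 points. The 469 are randomized subjects; the mITT set used for analysis excludes some of them, so 58.6 is an upper figure.

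**5. Plausible total.** The SAP gives no rate of missing items. Assume that 1-5% of HDA subjects reach the branch, and that 10-30% of those have a fall of exactly 4 or 5 and meet every other criterion.

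- Low end: 0.01 × 0.10 = 0.001, or 0.1 points; 52 × 0.001 = 0.05 subjects per arm.
- High end: 0.05 × 0.30 = 0.015, or 1.5 points; 52 × 0.015 = 0.78 subjects per arm.

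If both arms are inflated equally at the high end (31.5% against 56.5%), SRI-6 power moves from 0.631 to 0.627.

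**The case against.** The best defence is that Appendix 18.1.3 follows the drafting habit of Section 14.1.1. The only numbered criterion #1 there is the SRI-4 item, and SRI-6 is then obtained by putting 6 in place of 4. A programmer who carried that habit into the appendix would get the right answer, and the 6-point cut is unambiguous in both Section 14.1.1 and Section 14.1.2.2. The branch is also narrow. It needs a missing item, a failed carry-forward, a fall of exactly 4 or 5, and the PGA, BILAG and treatment-failure criteria all met. Clinical items are not expected to be missing, and a wholly missed visit is handled by a separate rule.

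Much of this stands. A reader might infer that the SAP orders a 4-point threshold for every SRI endpoint, or that subjects were in fact miscounted on SRI-6. The document supports neither. The rule never says that it covers every endpoint; that reading comes from its unqualified term and its reference to Section 14.1.1. Nothing shows which threshold was programmed. Nor is there any sign that missing items differ between arms, so a biased treatment comparison cannot be claimed.

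The defence does not remove the conflict. The appendix is named as a step in the primary analysis, its wording is not limited to SRI-4, and the multiple-imputation text shows that a separate SRI-6 threshold was thought necessary elsewhere. A program that used 6 in this branch would be sensible but would depart from the written rule.

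**Conclusion.** The point holds as an unadapted SRI-4 threshold in a rule that also serves SRI-6. If followed as written, it gives a result for 4- and 5-point falls that contradicts the plan's own SRI-6 definition. The conflict itself needs no numerical assumption.

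Its practical size does rest on assumptions. On the ranges above, fewer than one subject per arm is affected and power is essentially unchanged. One or two subjects falling in a single arm would shift that arm's rate by about 2 to 4 points, against a planned difference of 25. This is a correction to the wording of a primary endpoint, with a check on the program. It does not show that the reported result is wrong.

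**What to change.** Replace the two outcomes in Appendix 18.1.3 with a rule per endpoint: criterion #1 for SRI-X is met by a reduction of at least X points on the available items, with X = 4 for SRI-4, X = 6 for SRI-6 and the matching value for each bar in the SRI-4 to SRI-10 display. Any smaller reduction, no change or an increase is non-response for SRI-X. This follows Section 14.1.1 and introduces no new definition.

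SAP version 4.0 was written after the primary analysis had been reviewed (Sections 6.3 and 6.4), so changing the text is not enough. The sponsor should confirm which threshold the SRI-6 derivation used in this branch, report how many HDA subjects entered it at Week 52, and record the wording change as a correction. If 4 was used, the SRI-6 primary, sensitivity and secondary outputs should be rerun with 6. The cost is one line of text, one parameter and a check of the program, plus a documented rerun only if the check fails. The long-term-extension summaries should use the corrected rule.
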